3.5.3. Step 2: Produce Candidate Pool for Historical Cohort

EPI-Q will produce a candidate pool from which historical controls will be drawn via propensity match for comparison against the Furoscix Infusor cohort. This candidate pool will be comprised of HF-patient lives contained in the Marketscan Commercial Claims and Encounters (CCAE) and Medicare Supplemental Database. This pool will contain HF patients who will be characterized by binary indicators consistent with the demographic and background clinical variables (except laboratory tests) that are collected for the Furoscix Infusor arm (Appendix B).

Initially, the historical cohort will be created using the Marketscan Commercial Claims and Encounters (CCAE) and Medicare Supplemental Database for the years 2015-2017. The historical cohort will be later updated post acquisition of latest data up to year 2019.

The following inclusion criteria will be applied to identify patients with worsening HF:

1. Inpatient claims coded with an HF (ICD-9/ICD-10) diagnosis codes in primary position on the claim
2. Worsening HF defined by all admissions coded with a diagnosis-related group (DRG) for HF (291, 292, or 293)
3. Length of Stay 1-3 days
4. Service Category included ED Visit
5. Age 18-80 years
6. Continuous enrollment for 1 year before and 3 months after the index date
7. Background therapy including oral furosemide equivalents daily (Torsemide or Bumetanide)

First qualifying claim, where all the eligibility criteria is met, will be defined as the index date. Patients will be excluded if one of the following exclusion criteria is met:

1. Presence of diagnosis code for a complicating condition, other than HF (e.g. MI, pneumonia) as identified from the prospective arm data before final matching
2. Presence of diagnosis or procedure code for acute renal failure or Dialysis
3. Estimated Creatinine Clearance (CrCl) <30 (indicated by presence of diagnosis code for chronic kidney disease stage 4/5, ESRD or renal failure).

For the patients that meet all the eligibility criteria, the following demographic and baseline characteristics (i.e., candidate variables for propensity score calculation) will be determined and reconciled between the prospective study and historical controls' databases (i.e., only variables that can be consistently defined will be analyzed):

- Integer age
- Sex
- Geographic region (Northeast, North Central, South, West, Unknown)

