- Concomitant Medication Use in prior 3 months (90 days) of index or enrolment date (inclusive)
 - Oral Diuretic
 - Digoxin
 - ACE Inhibitors
 - Nitrates and hydralazine
 - Oral anticoagulant
 - Statin
 - Platelet Inhibitor
 - Beta Blockers
- Baseline conditions/co-morbidities in prior year (364 days) of index or enrolment date (inclusive)
 - Myocardial Infarction
 - Hypertension
 - Diabetes
 - Hyperlipidemia
 - Peripheral vascular disease
 - Arrhythmias
 - Malignancy
 - COPD
 - Stroke
 - Valvular heart disease
 - PCI
 - Acute Coronary syndrome
 - Chronic Kidney Disease Stage

- Baseline resource utilization (All-cause and HF-related) in the 6 months prior to index or enrolment date
 - Hospitalizations
 - ED Visits
 - Clinic Visits

Once the data have been reconciled, distributions of the candidate variables will be assessed. Variables will be excluded from the analysis if none of the subjects from the prospective arm have the characteristic or there is little variability. To maximize the number of subjects from the prospective arm, when discrete variables have missing data, an “unknown” category will be created. With respect to missing data for continuous variables, the population mean will be imputed.

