- A logistic regression model will be developed to estimate a propensity score for each subject. The model will include candidate variables (defined in Section 3.5.2 Step 2: Produce Candidate Pool for Historical Cohort). The dependent variable will be binary and indicate either prospective patient or historical control patient. Backwards stepwise selection will be implemented with alpha level of 0.1 or 0.20 to identify predictor variables of receiving Furoscix (prospective subject vs. historical control). The final model including candidate variables identified from backwards stepwise selection will be used to generate a predicated probability (propensity score of receiving Furoscix) for each subject.
- For treatment arm, the variables will be defined at time zero (enrollment/ED visit); for control patients, the variables will be defined at index as a possible match.
- Once final matches are identified, to assess balance in confounding variables between cases and controls, for each of the candidate variables included in the propensity score modeling, effect sizes (normalized difference between cases and controls) will be calculated based on the differences between the matched pairs. An effect size of <0.20 will be deemed acceptable.
- Control patients' data were weighted based on the number of controls within each matched treatment arm patient set. For instance, if a control patient was part of a set with 1 other control patient, each control patient in that set was weighted 0.50 (1 divided by the set count 2).
- In addition to the effect size evaluation, the baseline characteristics, i.e. all initial candidate variables for propensity model, between the two cohorts will be compared statistically and any variable difference with a p value of <0.1 will be identified.

Analyses, whether they be interim or final, will be conducted sequentially using the SEQTEST procedure in SAS, which has been specified elsewhere (SAS Institute, 2009). Briefly, The SEQTEST procedure performs interim and final

analyses by comparing test statistics with corresponding boundary values obtained with the SEQDESIGN procedure. If the information levels for the test statistics do not match the information levels obtained with the SEQDESIGN procedure, the SEQTEST procedure modifies the original boundary values to adjust for actual (observed) information levels.

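### A characteristic absent from every Furoscix subject is dropped from the propensity analysis with no general step to exclude controls who have it, and the 0.20 balance limit as worded may not cover it

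*SAP*

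**What the plan says.** SAP 3.5.3 (Step 2) lists the candidate variables: age, sex, region, 8 drug classes, 13 comorbidities and prior utilization. Once the two data sources are reconciled, it applies this rule: "Variables will be excluded from the analysis if none of the subjects from the prospective arm have the characteristic or there is little variability". The same section has one exclusion that draws on what the Furoscix arm shows: "Presence of diagnosis code for a complicating condition, other than HF (e.g. MI, pneumonia) as identified from the prospective arm data before final matching". Two further exclusions deal with renal disease.

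SAP 3.5.5 (Step 4) matches on a score difference of at most 0.01, exact sex, age within 5 years and a time-zero window. Two balance checks follow:

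- Effect sizes are calculated "for each of the candidate variables included in the propensity score modeling", "based on the differences between the matched pairs". The standard is "An effect size of <0.20 will be deemed acceptable".
- Separately, the matched groups are tested against each other on every initial candidate, whether or not it stayed in the model. The stated outcome is that "any variable difference with a p value of <0.1 will be identified".

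The SAP does not define the SD that standardizes the effect size, and it states no action after the second check.

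**The concern.** A characteristic with no carriers among the Furoscix subjects has no overlap for the controls who carry it. Omitting it from the logistic model is right, because zero carriers in one arm produce separation and the coefficient cannot be estimated. But omission alone leaves those controls eligible. None of the matching constraints acts on the trait directly, so the matched comparison can set 0% in the Furoscix arm against whatever rate remains in the controls.

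The first balance check, as worded, looks at variables in the propensity model, so the dropped one may escape it. If the trait is a comorbidity such as stroke or malignancy, controls who carry it plausibly have more readmissions and visits. Costs are built by summing benchmarks over events (SAP 3.5.3.1), so extra control events raise control cost, in the direction that favours Furoscix.

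**Working it through.** **Inputs.** Furoscix N of 10 and 34 evaluable at the interim analyses (SAP 3.5.5), with 75 as the expected upper limit (3.5.2). Matching ratio 1:1 to 4:1. Balance limit 0.20. The prevalence p of the dropped trait is an assumption throughout; the documents give none.

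**The plan's own N.** For a $2,100 difference, SD $3,045, 80% power and two-sided 5%: 2 × (3,045 × (1.960 + 0.842) / 2,100)² = 33.0 per group by the normal formula. The two-sample t-test gives 33.99, so 34. The stated N reproduces. It matters here only because a small arm makes zero counts common.

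**Standardized difference for 0 in Furoscix and p in matched controls.**

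- Pooled SD: d = p / √(p(1−p)/2) = √(2p/(1−p)).
- SD of 1:1 pair differences: d = √(p/(1−p)).
- SD of differences from the mean of 4 controls, taken as independent: d = √(4p/(1−p)).

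Setting d = 0.20 gives the prevalence at which the limit is reached: 0.02/1.02 = 1.96%, 0.04/1.04 = 3.85% and 0.01/1.01 = 0.99% respectively.

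**Chance that the rule is triggered.** If the Furoscix population has the same prevalence, P(no carriers) = (1−p)^N.

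| p | d, pooled SD | d, 1:1 pair SD | P(zero), N=10 | P(zero), N=34 |
|---|---|---|---|---|
| 1% | 0.14 | 0.10 | 90% | 71% |
| 2% | 0.20 | 0.14 | 82% | 50% |
| 3% | 0.25 | 0.18 | 74% | 36% |
| 5% | 0.32 | 0.23 | 60% | 17% |
| 10% | 0.47 | 0.33 | 35% | 2.8% |
| 20% | 0.71 | 0.50 | 11% | 0.05% |

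**Would the p<0.1 comparison catch it?** These are the smallest carrier counts among matched controls at N=34, with none in the Furoscix arm:

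| Ratio | Exceeds 0.20 (pooled SD) | p<0.1, chi-square | p<0.1, Fisher |
|---|---|---|---|
| 1:1 | 1 of 34 (d = 0.246) | 3 of 34 (8.8%) | 5 of 34 (14.7%) |
| 4:1 | 3 of 136 (d = 0.212) | 11 of 136 (8.1%) | 13 of 136 (9.6%) |

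With a pooled SD, an imbalance from a control prevalence of about 2% to 8% would exceed 0.20 and still pass the significance comparison.

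**After restriction.** If controls with the trait are removed before matching, prevalence is 0 in both arms and d is exactly 0.

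**The case against.** Several points on the other side have force.

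- A reader might infer that the rule guarantees a breach of 0.20. It does not. With the SD of 1:1 pair differences, which the SAP's wording about matched pairs could mean, 3% prevalence gives 0.18. Matching on age, sex, related diagnoses and prior utilization may also pull the trait's rate in matched controls below its rate in the pool.
- A reader might infer that dropped variables go unexamined. They do not: the p<0.1 comparison covers every initial candidate. What stands is that it has little power at these sizes and leads to no stated action.
- Control exclusion 1 already restricts the pool by what the Furoscix arm shows, and its first example, MI, is also on the comorbidity list. Its scope is unclear, and it does not plainly reach the other comorbidities, the drug classes, region or prior utilization.
- Not every listed variable can be zero. Background oral diuretic is required in both arms.
- The rule is triggered mainly by rare traits, where cost bias is small. If carriers cost a full SD more ($3,045, an assumption), one trait shifts the control mean by 3% × $3,045 = $91 or 5% × $3,045 = $152, which is 4% or 7% of the $2,100 effect. At 10% it is $305 (15%), but a zero count at N=34 then has a chance of only 2.8%.

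The last point limits the importance of any single trait. It does not remove the gap, since several traits could be dropped at once and selection into the Furoscix arm could make zeros more frequent than chance.

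**Conclusion.** The point holds in limited form. The SAP drops a characteristic that no Furoscix subject has, provides no general restriction of the controls who have it, and words its 0.20 limit so that the dropped variable may fall outside it. The imbalance exceeds 0.20 once about 2% of matched controls carry the trait with a pooled SD, or about 1% to 4% under the other SDs the text allows. At an assumed 5% prevalence the rule is triggered with a chance of 60% at N=10 and 17% at N=34.

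The documents do not support a firm statement about bias in the cost result. For comorbidities the direction plausibly favours Furoscix; for drug classes it is uncertain; and the size depends on prevalences and carrier costs that are not given. This is an inexpensive improvement to the matching plan, not evidence that the primary comparison is wrong.

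**What to change.** Replace the dropping rule in SAP 3.5.3 with a restriction, and widen the balance check in 3.5.5:

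1. At each analysis, before fitting the model, exclude from matching any control with a listed characteristic that no Furoscix subject has. Where all Furoscix subjects have a characteristic, keep only controls who have it. Then omit the now-constant variable from the logistic model.
2. Derive the cost benchmarks of 3.5.3.1 from the pool before this filter. Those benchmarks are applied to both arms, so filtering first could change the costs assigned to everyone.
3. Report the standardized difference for every initial candidate variable, define its SD, apply the 0.20 limit to all of them, and state what follows if it is exceeded. This also covers variables dropped for little variability that are not constant.
4. Say how a filter applied at each analysis fits with the statement in 3.5.5 that the final match reuses the algorithm of the last interim analysis.

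The cost is one filter step and a few sentences. The downsides are some loss of controls, which cannot be sized because no pool count is given, and a matched pool that may differ between the N=10, N=34 and final analyses.

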3.5.3.1. Healthcare Resource Utilization (HCRU) and Costs

For each patient in the historical control and prospective arm, 30-day follow-up HF-related and all-cause healthcare resource utilization (HCRU) will be estimated and reported.

For cost inputs, events that are major contributors of the costs will be included in the analysis, including any visits and hospitalizations that are either HF-related or all-cause. Using the dataset created for matching, cost benchmarks for each event (HF-related and all-cause) i.e. mean and standard deviation will be derived. For each patient in the historical and prospective cohorts, 30-day HF-related and overall costs will be estimated by summation of applied cost benchmarks to each resource utilization event observed during the 30-day period starting from the beginning of HF-worsening episode.

Overall cost of care will include cost attribute to all-cause HCRU. Total HF-related medical costs will be comprised of the hospitalization costs and outpatient visits costs attributable to HF-related HCRU (defined by claims with a primary diagnosis of HF). All costs will be inflated to \$2019 using Medical Care Consumer Price Index (CPI). All costs included will be gross costs including payer and patient costs.

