2. STUDY OBJECTIVES

The objectives of this study are:

1. To evaluate differences in healthcare resource utilization costs for subjects treated with the Furoscix Infusor outside the hospital compared to patients receiving intravenous furosemide for ≤ 72 hours in the hospital setting for 30 days post-discharge from the emergency department.
2. To evaluate the safety of Furoscix administered outside the hospital.
3. To evaluate and describe quality of life and patient satisfaction for patients who receive the Furoscix Infusor outside the hospital setting.

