6. STUDY PROCEDURES

6.1. Study Measurements and Assessments

6.1.1. Assessment of Primary Endpoint

The difference in the overall and heart failure related healthcare costs between subjects treated with the Furoscix Infusor through 30 days post discharge from the emergency department compared to propensity score matched controls treated in the hospital for \leq 72 hours through 30 days post discharge. Overall and heart failure related healthcare costs comprised of all direct medical costs attributable to healthcare resource utilization incurred overall and for treatment of HF.

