8. STATISTICS

8.1. Determination of Sample Size

Based on an average hospital cost of a patient hospitalized for \leq 72 hours with a primary diagnosis of HF (Diagnosis Related Group Code 291, 292 and 293) of \$8,600 (standard deviation: \$3,045), 68 patients (34 in each group) are required to have an 80% chance of detecting a decrease in hospital costs to \$6,500 at a significance level of 5%. The target sample size of the Furoscix cohort will initially be N=34 subjects.

Given the anticipated overdispersion of the primary outcome (i.e., difference in total HF-attributable direct medical costs), we will employ adaptive trial design procedures for sample size re-estimation. This adaptive-total information criterion approach was taken due to the risk of incorrectly estimating the sample size due to misspecification of the cost outcome parameters. By using the adaptive sample size design, which includes no penalty for repeated interim analysis, the final sample size will be sufficient to provide adequate power to test the stated hypothesis.

This will include re-assessment of the sample size at N=34 in the Furoscix cohort by using a group sequential design and testing to allow for stopping. It is not expected that the sample size for the Furoscix Infusor arm would exceed N=75, but the maximum value cannot be definitively stated until the analysis at N=34 is completed.

We will explore ratios ranging from 1:1 to 4:1 for the number of historical controls to be matched to Furoscix-treated patients using methods reported by Millar and Pasta 2010. The simulations will be used to find the matching ratio at which the level of precision is optimized without biasing the variance of the outcome measure. Additional methodological details are described in the prespecified statistical analysis plan.

The methodology by which the sample size will be re-estimated and stopping rules will be implemented will be detailed in the statistical analysis plan.

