3.3.5. Trial Design

A group sequential design is being employed to allow for stopping due to futility or efficacy. This design includes the following general steps (cite SAS manual for group sequential designs):

1. Specify the statistical details of the design, including the null and alternative hypotheses (null hypothesis being that there is no difference in 30-day HF-related direct medical costs between the Furoscix Infusor and historical control arms), a test statistic for the hypothesis test, the Type I and II error probabilities, a stopping criterion, the total number of stages, and the relative information level at each stage.
2. Compute the boundary values for the trial based on the specifications in Step 1 and compute the sample size required at each stage for the specified hypothesis test.
3. At each stage, collect additional data with the required sample sizes. This includes the data collected at the current stage in addition to the data collected at previous stages.
4. At each stage, analyze the available data and compute the test statistic.
5. At each stage, compare the test statistic with the corresponding boundary values. The trial will stop to reject or accept the hypothesis, or it will continue to the next stage.
6. Once the trial stops, parameter estimates, confidence limits for the parameter, and a p-value for the hypothesis test are computed.

Below is a depiction of a hypothetical 4-stage design with two-sided testing.

Figure 1. Boundaries for Two-Sided Group Sequential Test

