3.5.4. Step 3: Compute Boundary Values for Primary Outcome

Boundary values for the primary outcome will be derived via the SEQDESIGN (REF SAS SEQDESIGN) procedure in SAS; specifically using a two-sided O’Brien Fleming design which has conservative stopping boundary values at early stages, and boundary values at the final stage that are close to the fixed-sample design. This produces a conservative design because compared to other approaches, the O’Brien-Fleming approach makes it more difficult to reject the null hypothesis in early stages than in later stages (null hypothesis being that there is no difference in 30-day HF-related direct medical costs between the Furoscix Infusor and historical control arms).

Assume that the total 30-day HF-related direct medical costs are normally distributed with means μ_e and μ_c for individuals in the Furoscix Infusor and historical control groups, respectively. The null hypothesis of no effect for the Furoscix Infusor is $H_0 : \theta = 0$, where $\theta = \mu_e - \mu_c$

The specific procedure for determining the boundary values for the primary outcome are specified elsewhere (REF SAS SEQDESIGN). Utilizing this procedure requires that we prespecify the meaningful difference between groups and the standard deviation thereof in order to achieve the specified power. The boundary values will be estimated based on a difference of \$2,100 (based an average hospital cost of a patient hospitalized for ≤ 72 hours with a primary diagnosis of HF (Diagnosis Related Group Code 291, 292 and 293) of \$8,600 (standard deviation: \$3,045), 68 patients (34 in each group) are required to have an 80% chance of detecting a decrease in hospital costs to \$6,500 at a significance level of 5%).

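### HF-related cost, the quantity in the null hypothesis, does not charge the study product on the visible text, and no passage labels the result as excluding it

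*SAP*

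**What the plan says.** **What is tested.** SAP 3.3.5 states the hypothesis as "null hypothesis being that there is no difference in 30-day HF-related direct medical costs between the Furoscix Infusor and historical control arms", and SAP 3.5.4 builds the sequential boundaries on the same quantity: "Assume that the total 30-day HF-related direct medical costs are normally distributed". The primary analysis in SAP 3.5.1 also covers overall cost of care.

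**How it is costed.** SAP 3.5.3.1 gives the contents of HF-related cost: "Total HF-related medical costs will be comprised of the hospitalization costs and outpatient visits costs attributable to HF-related HCRU". The unit costs come from claims: "Using the dataset created for matching, cost benchmarks for each event (HF-related and all-cause"). Each patient's cost is the sum of these benchmarks over the events seen in 30 days. SAP 3.5.3 takes the claims from a commercial and Medicare supplemental database, later updated to 2019. For the other component, SAP 3.5.3.1 says "Overall cost of care will include cost attribute to all-cause HCRU".

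**How the endpoint is described.** Protocol Section 2, Objective 1, reads "To evaluate differences in healthcare resource utilization costs for subjects treated with the Furoscix Infusor outside the hospital". Protocol 6.1.1 describes the costs as "comprised of all direct medical costs attributable to healthcare resource utilization incurred overall and for treatment of HF". Protocol 8.1 drops the reference to utilization: "Given the anticipated overdispersion of the primary outcome (i.e., difference in total HF-attributable direct medical costs"); the Synopsis (Number of Subjects) does the same.

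**The product.** Protocol 5.2 calls it an investigational drug-device combination. Protocol 6.2 expects about 4 doses before return to oral diuretic and limits use to 7 in 30 days unless the medical monitor approves more. Neither document gives a price, says that product cost is added, or says that it is left out.

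**The concern.** The comparison sets treatment at home with the study product against a short hospital stay. The stay is costed. In HF-related cost the product that replaces it appears not to be, and only one arm uses it. Any positive price would reduce the saving, so the omission has one direction.

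A comparison of utilization costs is a legitimate question. The difficulty is in how the answer will be worded. If the null is rejected, the documents' own language supports a statement that HF-related direct medical costs were lower with Furoscix. A payer could reasonably take that as a net saving, and nothing in either document warns that the treatment under test was counted as free.

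**Working it through.** **1. Is the product charged? The passages side by side.**
- HF-related cost (SAP 3.5.3.1): the list contains hospitalization and outpatient visits. It has no drug, device or product item.
- Unit costs (SAP 3.5.3, 3.5.3.1): benchmarks from claims no later than 2019. A product that the protocol still calls investigational would have no claims event to price.
- Overall cost (SAP 3.5.3.1): says only what it will include. No product term is shown, but the list is not closed.
- Exclusion statement: none found in either document.

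So for HF-related cost, non-charging follows from the closed list and the price source. For overall cost the text does not settle it.

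**2. The plan's own figure.** Inputs from Protocol 8.1 and SAP 3.5.2: means $8,600 and $6,500, SD $3,045, 80% power; two-sided 5% from SAP 3.3.3.
- Difference = 8,600 − 6,500 = $2,100.
- n per group = 2 × [(1.960 + 0.842) × 3,045 / 2,100]² = 33.005, rounded up to **34**. The exact t-test also needs 34, with power 80.0%.

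The stated 34 per group reproduces. This point does not touch the sample-size arithmetic. It concerns what the $2,100 contains.

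**3. Break-even price.** Let p be the price per dose and d the mean doses per Furoscix subject. Net saving = 2,100 − d × p, which is zero at p = 2,100 / d.
- d = 4: 2,100 / 4 = **$525** per dose.
- d = 7: 2,100 / 7 = **$300** per dose. This is the case in which every subject uses the limit; 7 is a per-subject limit, not a mean.

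Net saving over a range of prices, all of them assumptions:

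| Assumed price per dose | 4 doses | 7 doses |
|---|---|---|
| $50 | $1,900 | $1,750 |
| $100 | $1,700 | $1,400 |
| $200 | $1,300 | $700 |
| $300 | $900 | $0 |
| $525 | $0 | −$1,575 |

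**4. Why no price is given at which significance is lost.** A simple two-sample calculation at 34 per group has SE = 3,045 × √(2/34) = $738.5. With t = 1.9966 on 66 df, the 95% half-width is $1,474.5 and the lower limit for a $2,100 saving is $625.5, or $156 per dose at 4 doses. That is not the planned analysis. The plan uses matched sets, a paired t-test or signed-rank test, and O'Brien-Fleming boundaries, and SAP 3.5.5 makes N=34 an interim look. With looks at 10, 34 and an assumed maximum of 75, the boundary at 34 is about |z| = 2.91 to 2.93, depending on the form of the O'Brien-Fleming rule. At 1:1 the planning difference gives z = 2,100 / 738.5 = 2.84, which does not cross it. The SD is also that of hospital cost, not of summed benchmarks. Only the break-even figures are free of these choices.

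**The case against.** **The scope is already visible.** SAP 3.5.3.1 lists the components in advance, the list fits Objective 1 and the stated purpose of studying hospital avoidance, and the Protocol 6.1.1 definition is tied to healthcare resource utilization. On this view only a wording request remains. Much of this stands: the endpoint is legitimate and its contents are pre-specified. What does not go away is that the 6.1.1 qualifier does not mention product, and that the hypothesis and sample-size passages omit the qualifier.

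**The protocol and SAP definitions conflict.** A reader might infer this, taking Protocol 6.1.1 as covering every direct medical cost. The documents do not support it: with its qualifier, 6.1.1 can be read consistently with the SAP list.

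**Both cost measures omit the product.** A reader might infer this too. For overall cost the wording is open, so the most that can be said is that the treatment of product is unclear. Even for HF-related cost the omission is inferred, and the appendices (codebook and CRF) cannot be consulted. If they do add the product, SAP 3.5.3.1 should say so.

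**An investigational product has no price.** True, and a reason not to put one in the primary analysis. A break-even figure needs none.

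**Other items are missing as well.** Also true. The HF-related list has no outpatient drug item in either arm, so study product is one omitted item and not the whole net error. That a control patient's inpatient diuretic is covered by the admission benchmark is itself an inference.

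**Conclusion.** The point holds as a matter of scope and labelling. On the visible text, HF-related cost excludes the study product, nothing says so, and the unqualified direct-medical-cost wording in the Protocol Synopsis, Protocol 8.1, SAP 3.3.5 and SAP 3.5.4 invites a net-saving reading that the calculation would not support. The omission falls on one arm and favours Furoscix at any positive price.

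Its size is unknown because no price is given. The only robust illustration is break-even at $525 per dose (about 4 doses) or $300 (7 doses for every subject). It rests on $2,100 as the saving, which is a planning value and not an expected result.

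Two stronger conclusions might be drawn and should not be. One is that the primary test is invalid: it remains a valid question about utilization cost. The other is that significance disappears at some particular price per dose: such thresholds depend on a fixed-sample, independent-groups test that the plan does not use. The point is worth correcting because the omission bears on the main economic conclusion and the correction is cheap.

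**What to change.** 1. In SAP 3.5.3.1, state that HF-related cost excludes study product, and state whether overall cost does.
2. Carry that label into the reported primary result and its conclusion.
3. Pre-specify one supporting analysis: break-even price per dose = (mean control cost − mean Furoscix cost) / mean recorded doses. Give a confidence interval, for example by bootstrap over matched sets so that costs and doses are resampled together. Say in advance how a zero or negative saving will be reported. A table over assumed prices is optional.

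The primary test, the boundaries and N=34 stay as they are.

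**Cost.** SAP text and a small amount of programming. No new data are needed: the diary records each infusion (Protocol 6.2.2) and dispensing is documented (Protocol 9.1.11). Changing Protocol 6.1.1 now would require an amendment with IRB approval (Protocol 9.2.2). SAP text is enough, and 6.1.1 can be aligned at the next amendment. The sponsor gives up some breadth in the conclusion.
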